#### 10.7.10 Plasma Samples for Iohexol

Blood sample (4 mL) for the determination of plasma iohexol levels will be collected into lithium heparinized tube(s) per time-point as specified in Table 8.

Full details of sample handling and processing can be found in the SHM.

#### **10.7.11 Urine Samples for Iohexol**

Urine samples will be collected for the determination of iohexol in urine at the time-points specified in Table 8.

Each urine collection container will be identified with a barcoded label bearing details of the study number, subject number, sampling time-point, sample type (*i.e.* sample matrix, *e.g.* blood, etc.), and a unique 9-digit identification number.

- Only a single urine void is required pre-dose, each subject will collect one sample pre-dose (ideally the first void of the day prior to dosing). Subjects will be encouraged to empty their bladder immediately prior to dosing; however, this void will not be required to be collected if a sample has already been produced (first void of the day).
- The urine collection containers will be kept chilled (at approximately 4°C) during the collection intervals.
- At the end of the collection timepoint, the bulk sample should be weighed (g) and the volume calculated (v). Once weighed, thoroughly mix the urine and immediately, using a Gilson pipette, transfer 10 mL of urine into 2 appropriately labelled polypropylene tubes.
- 2 x 10 mL aliquots will be transferred immediately to the -20°C freezer until shipment for analysis.

Full details of sample handling and processing can be found in the SHM.

Confidential

Page 94 of 109

DNDi RD 777/34920 DNDi- 0690- 02

Final V3.0/ Date 07 December 2020

#### 10.7.12 Urine Samples for Exploratory Biomarkers

Urine samples (from PK urine samples or spot collection) will be collected for the following exploratory markers at the time-points specified in Table 6, Table 7 and Table 8.

- Kidney Injury Molecule-1 (KIM-1)
- Neutrophil Gelatinase-Associated Lipocalin (NGAL)
- Cystatin C (Cys C)

Urine samples for the determination of exploratory biomarkers will be collected from a morning spot urine sample or at the time of urine collection for safety sampling.

2 x 20 mL samples of urine will be aliquoted from the bulk urine in to 2 appropriately labelled 25 mL polypropylene tubes immediately after the urine has been mixed. These aliquots must be taken after the bulk sample has been weighed and volume calculated. Samples should be stored at -80°C until shipment

After all aliquots for bioanalysis, urine iohexol analysis and exploratory biomarkers for each collection timepoint have been removed, the remaining bulk sample will be discarded.

# Analysis of urine exploratory biomarkers will be optional and a decision to analyse those samples will be made by DNDi at the end of the study.

The biomarkers will be analysed by Simbec-Orion Laboratories if required. For biomarker tests the urine creatinine level is also required in order to normalise the data to account for differences in urine volume of a sample.

- o Urine NGAL levels will be measured on the automated Roche c501 immunoassay platform using commercially available Bioporto NGAL immunoassay kit reagents.
- Urine Kim-1 level will be measured using a commercially available R&D System ELISA kit.
- Urine Cys C level will be measured using a commercially available R&D System ELISA kit.

The exploratory biomarker samples will be batched prior to analysis.

Full details of sample handling and processing can be found in the SHM.

#### 10.7.13 Other Assessments

N/A

# **10.8 Data Quality Assurance**

At the time the study is initiated, a representative of the Sponsor will thoroughly review the final protocol and CRFs with the PI and site staff. During the course of the study the Monitor will visit the Clinical Unit regularly to check the completeness of the subjects' records (including the volunteer (subject) master files, laboratory and 12-lead ECG print-outs), the accuracy of entries into the CRFs, the adherence to the final protocol and to ICH GCP E6 (R2) guidelines, the progress of enrolment and also to ensure the storage, handling and accountability of the IMP. The PI and key study personnel will be available to assist the Monitor during these visits.

Confidential

RD 777/34920 DNDi- 0690- 02

**DNDi** 

Final V3.0/ Date 07 December 2020

Page 95 of 109

The PI will give the Monitor, Auditor(s), Sponsor representatives, the REC, and the MHRA direct access to relevant clinical records to confirm their consistency with the CRF entries. No information in these records about the identity of the subjects will leave Simbec-Orion. The Sponsor will maintain the confidentiality of all subject records, in line with Section 6.10 of the ICH GCP E6 (R2) guidelines.

Study data will be fully documented in the CRFs and study logbooks. Dated signatures will be given to account for all interventions in the study by research staff.

Source data is all information in original records and certified copies of original records of clinical findings, observations, or other activities in a clinical study necessary for the reconstruction and evaluation of the study. Source data are contained in source documents (original records or certified copies).

For the purposes of this study the source data will be recorded as detailed in Table 10.

Confidential

RD 777/34920 DNDi- 0690- 02

**DNDi** 

Final V3.0/ Date 07 December 2020

Page 96 of 109

#### **Table 10** Summary of Source Documentation Location

Data	Source Document								
	Volunteer Master File	eCRF  *	Paper Workbook	Other					
Evidence of healthy subject status/primary	X								
disease condition for entry into clinical study									
Demographic data		X							
Medical and surgical history and age	X								
Inclusion and exclusion criteria/subject eligibility 		X	X						
Informed consents 		X		X					
Subject participation in the clinical study		X							
Screening number				X (Screening log)					
Subject number				X (Enrolment log)					
AEs		X							
SAEs				X (SAE form)					
				X (Pregnancy					
Pregnancies				notification and					
				outcome form)					
Previous and on-going therapy	X	X							
Concomitant medication		X							
Meals start and stop time				X (Meal Logbook)					
Daily water consumption volume				X (Water Intake Logbook)					
Results of study examinations (e.g. physical		X		X					
examination, 12-lead ECGs, vital signs and									
laboratory safety tests) 									
Study visit dates		X							
Administration of IMP		X							
Blood PK sample collection times		X							
Urine PK sample collection times (including				X (logbook)					
start and stop times of collection intervals and				,					
volumes)									
Blood safety sample collection times		X							
Urine safety sample collection times				X (logbook)					
(including start and stop times of collection									
intervals and volumes)									
ECG Holter				X (Holter					
				extractions)					
Physical examination 		X							

In the event staff are unable to enter data directly into the eCRF (*e.g.* technical/internet issues), data will be entered directly into a back-up paper source workbook at the time of assessment, then transcribed and subsequently QC'd by Simbec-Orion clinical staff.

CRF = case report form, ECG = electrocardiogram, PK = pharmacokinetic

<sup>2. Subject eligibility for this study will be captured in an inclusion/exclusion table found in the paper Source Workbook.

3. The original informed consent forms will be maintained in the study officer file during the clinical phase and will then be transferred to the Project Manager for archiving with the Investigator site file at the end of the study. Details of consent *e.g.* date, version, Physician who consented, will be entered on eCRF.

4. The 12-lead ECG trace and laboratory safety test print-out including medical review will be stored with the Source Data Files

5. The date and time of each physical examination will be recorded in the eCRF. Abnormal physical examination results will be recorded on medical history page at Screening or on AE page post dosing.

DNDi RD 777/34920 DNDi- 0690- 02

Final V3.0/ Date 07 December 2020

Confidential

Page 97 of 109

The above table indicates where source data will be recorded but for completeness the following information will also be recorded in the volunteer master file:

- Clinical study code.
- Study visit dates (pre-dose; post-dose).
- IMP administration (date of last dose).
- Results of any key safety measures from the clinical study that, in the opinion of an Investigator, should be noted.
- Any concomitant medications used to treat the subject during the study that, in the opinion of an Investigator, should be noted.

The data collected in the CRFs during the study will be subject to quality control checking by clinical staff and monitor checks prior to sign off.

Designated Investigator site staff will enter the data required by the protocol directly into the electronic CRFs (e-CRFs) using fully validated software that conforms to 21 CFR Part 11 requirements. Staff will not be given access to the eCRF until they have been trained. Automatic validation programs check for data discrepancies and, by generating appropriate error messages, allow the data to be confirmed or corrected before transfer of the data to the Biometrics group. The Investigator must certify that the data entered into the e-CRF are complete and accurate.

The study will be subject to an independent audit by the Simbec-Orion Quality Assurance Unit as outlined in Simbec-Orion SOPGRP-QA 002.

Independent clinical quality assurance audits may be performed at any time during or following completion of the study by the Sponsor, or its authorised agents, and Regulatory Authorities and/or the REC.

# 10.9 Statistical Methods and Determination of Sample Size

#### 10.9.1 Statistical Analysis Plan

A statistical analysis plan (SAP) will be written by Simbec-Orion and agreed by DNDi prior to the locking of the database and subsequent reporting of the study data.

# 10.9.2 Study Variables/Endpoints

#### 10.9.2.1 Primary Endpoints

Safety parameters (changes in vital signs, ECG, safety laboratory parameters with special focus on renal function parameters, *i.e.* serum creatinine, blood urea nitrogen (BUN), and Cys C), and frequency and severity of observed TEAEs.

#### 10.9.2.2 Secondary Endpoints

Measurement of the following PK parameters:

• Day 1:

DNDi RD 777/34920 DNDi- 0690- 02

Final V3.0/ Date 07 December 2020

Confidential

Page 98 of 109

- o Main: Cmax, Cmax/D, AUC0-24, AUC0-24/D
- $\hspace{0.5cm} \circ \hspace{0.5cm} Exploratory: AUC_{0\text{-}24,norm}, \hspace{0.5cm} C_{max,norm}, \hspace{0.5cm} T_{max}, \hspace{0.5cm} MRT_{last} \\$
- Day 10:
  - o Main: AUC0-inf, AUC0-inf/D, AUC0-24, AUC0-24/D, Cmax ss, Cmax ss/D, Cmin SS
- Exploratory: AUC0-inf,norm, AUC0-24,norm, AUClast, AUClast/D, AUClast,norm, Cmax ss,norm, Tmax, t1/2, Cl/F, lambda-z, MRTlast, Vz/F, CLss/F and points terminal for DNDI-0690
- Optional: if BID dosing, AUC0-10, AUC0-10/D, AUC0-10,norm will be added on Day 1 and Day10
- AUCt-inf, %AUCextra, points terminal
- Accumulation ratios RA(Cmax) and RA(AUC0-tau) will be calculated
- $C_{trough}$  will be derived from the concentration data (Days 2 10, Part A, days 2/4/5 for Part B and days 2/4/7/10 for Part C)
- Measurement of the urine PK parameters Ae, Ae% and CLR for DNDI-0690
- Glomerular filtration rate measurement (mGFR) following evaluation of plasma clearance of iohexol before and under exposure to DNDI-0690

#### 10.9.2.3 Exploratory Endpoints

- Changes in clinical early renal toxicity markers in urine: Cystatin C (Cys C), Kidney Injury Molecule-1 (KIM-1), neutrophil gelatinase-associated lipocalin (NGAL).
- Analysis of Holter extracted ECGs for the following parameters: RR, heart rate (HR), PR, QRS, QT, corrected QT interval by Fridericia's formula (QTcF), corrected QT interval by Bazett's formula (QTcB), ΔHR, ΔRR, ΔPR, ΔQRS, ΔQT, ΔQTcF and ΔQTcB.
- Measurement of drug concentration in dry blood spots for comparison with matching plasma samples.
- Variation of mRNA expression in blood sample before and after exposure to the drug (Transcriptional Profiling).
- Exploration of metabolism after multiple dose exposure.

#### 10.9.2.4 Analysis Sets

**Safety Set:** All randomised subjects who receive at least 1 dose of IMP will be included in the safety analysis.

**PK Set:** Subjects will be assigned to the PK set on a per treatment basis. Randomised subjects will be assigned to the PK set for a particular treatment where they have received the specific treatment and comply with the following criteria:

Do not have an occurrence of vomiting (that occurs at or before 2 times median Tmax within the appropriate cohort or treatment) or diarrhoea which renders the concentration profile unreliable,

DNDi RD 777/34920 DNDi- 0690- 02

Final V3.0/ Date 07 December 2020

Confidential

Page 99 of 109

- Do not have an occurrence of vomiting (during a period of time less than or equal to the dosing interval) or diarrhoea which renders the concentration profile unreliable,
- Do not use a concomitant medication which renders the concentration profile unreliable,
- Do not have a pre-dose concentration that is greater than 5% of the corresponding  $C_{max}$ ,
- Have at least one pharmacokinetic sample with concentration above the lower limit of quantitation (LLOQ),
- Do not violate the protocol in such a way that may invalidate or bias the results (major protocol violators).

#### 10.9.2.5 Description of Statistical Methods

All statistical analysis will be performed using SAS® (the most up to date version will be used and this will be documented in the DMP/SAP).

# 10.9.2.5.1 Demographic and Background Data

All demographic and background data will be listed, in addition:

**Disposition:** Subject disposition will be listed with any withdrawals flagged. Frequencies (number and %) of the total number of subjects dosed, completed and prematurely discontinued (including reason for discontinuation) from the study will be summarised. Additionally, the frequency of subjects within each analysis set will be summarised.

**Demographics:** Demographic data will be listed. Descriptive statistics (number of subjects in the analysis set (N), number of subjects with non-missing observations (n), mean, standard deviation (SD), minimum, median and maximum) will be tabulated for the continuous variables age, height, weight and BMI and frequencies (number and %) for the categorical variable race.

#### **10.9.2.5.2** Efficacy Data

N/A

#### 10.9.2.5.3 Safety Data

All safety data will be listed, in addition:

**AEs:** All AEs will be coded using the Medical Dictionary for Regulatory Activities (MedDRA) dictionary (the most up to date version that is available at the time of database build will be used and will be listed in the DMP). The MedDRA dictionary will not be updated during the course of the study.

All AEs and SAEs, including those which occurred prior to the first dose of IMP, will be listed. Only TEAEs, *i.e.* existing conditions that worsen or events that occur during the course of the study after administration of IMP, will be included within the summary tables.

An overall summary of AEs will be produced including the number of TEAEs; the number and % of subjects reporting at least 1 TEAE, serious TEAE, TEAE leading to withdrawal from the study; the number and % of subjects reporting TEAEs by severity and relationship to IMP.

DNDi RD 777/34920 DNDi- 0690- 02

Final V3.0/ Date 07 December 2020

Confidential

Page 100 of 109

The number of TEAEs and the number and % of subjects reporting at least 1 TEAE will be tabulated by system organ class (SOC) and preferred term. A subject reporting multiple episodes of a particular AE within a treatment period will only contribute 1 count towards the corresponding SOC and preferred term.

The number of TEAEs and the number and % of subjects reporting at least 1 TEAE will be tabulated by preferred term and sorted by descending frequency on the total number of subjects with that AE. A subject reporting multiple episodes of a particular AE within a treatment period will only contribute 1 count towards the corresponding preferred term.

In addition, the number and % of subjects reporting TEAEs will be tabulated by maximum severity and strongest relationship to IMP. For the summary of TEAEs by severity, if a subject has multiple events occurring within the same SOC or preferred term the event with the highest severity will be counted. Similarly, for TEAEs by relationship to IMP, if a subject has multiple events occurring within the same SOC or preferred term, the event with the highest association to IMP will be counted.

**Laboratory Safety:** Biochemistry, haematology, coagulation, and urinalysis parameters will be listed with any out of normal range values flagged. Laboratory test results which are out of normal range will also be presented separately along with normal reference ranges. Descriptive statistics (N, n, mean, SD, minimum, median and maximum) of absolute and change from baseline (Day -2) values at each protocol-defined time-point will be tabulated.

**Vital Signs:** Vital signs parameters will be listed with any out of normal range values flagged. Descriptive statistics (N, n, mean, SD, minimum, median and maximum) of absolute and change from baseline (Day 1 pre-dose) values at each time-point will be tabulated.

**12-Lead ECG:** 12-Lead ECG parameters will be listed with any out of normal range values flagged. Descriptive statistics (N, n, mean, SD, minimum, median and maximum) of absolute and change from baseline (Day 1 pre-dose) values at each time-point will be tabulated.

Additionally, the frequency (number and % of subjects) for absolute and change from baseline QTcB and QTcF values will be summarised according to the below categories:

#### For absolute values

- QTcB/QTcF  $\leq$  450 msec.
- QTcB/QTcF > 450 msec and QTcB/QTcF ≤ 480 msec.
- QTcB/QTcF > 480 msec and QTcB/QTcF  $\leq$  500 msec.
- QTcB/QTcF > 500 msec.

#### For change from baseline

- QTcB/QTcF  $\leq$  30 msec.
- QTcB/QTcF > 30 msec and QTcB/QTcF  $\leq$  60 msec.
- QTcB/QTcF > 60 msec.

Confidential

Final V3.0/ Date 07 December 2020 Page 101 of 109

DNDi RD 777/34920 DNDi- 0690- 02

#### 10.9.2.5.4 PK Data

Concentration-Time Data: Individual plasma DNDI-0690 concentration-time data will be listed. Concentration-time data will also be summarised. The descriptive statistics presented will be N, n, arithmetic mean, geometric mean, SD, coefficient of variation (CV%), minimum, median and maximum. Individual and mean concentration-time data will also be plotted on both linear and semi-logarithmic scales.

For the purposes of summarising and plotting concentration-time data, concentration value(s) below the LLOQ will be assigned a value of zero if the timepoint is prior to treatment and LLOQ/2 otherwise.

In addition, an investigative plasma analysis will be performed to further evaluate a potential metabolite M5 (no chemical structure could be assigned but likely formed via di-oxidation and nitro-reduction) which was detected in plasma of preclinical species and in exploratory investigations in humans. However, absolute circulating amounts of M5 remain unknown since no reference standard of M5 is available due to its instability following chemical synthesis.

**Derived PK Data:** The following PK parameters will be derived from plasma DNDI-0690 concentration-time data following administration of IMP using Phoenix WinNonlin (the most up to date version will be used and this will be documented in the SAP).

For the purposes of calculating PK parameters, concentration value(s) below the LLOQ will be assigned a value of zero.

#### • Day 1 (Part A and Part B):

- o Cmax: Maximum concentration
- o Cmax/D: Maximum concentration/Dose
- o AUC0-24: Area under the concentration-time curve (AUC) from the time of dosing to 24 hours pose
- o AUC0-24/D: AUC0-24/Dose
- o AUC0-24, norm: Area under the concentration versus time curve from zero to 24 hours divided by dose per kilogram body weight
- o Cmax, norm: Maximum concentration divided by dose per kilogram body weight
- o Tmax: The time to maximum observed concentration
- o MRTlast: Mean Residence Time from the time of dosing to the time of the last measurable concentration
- Ae0-24: Amount excreted in urine over each collection interval (0 to 24 hours post-dose).
- Ae%: % of dose excreted in urine over each collection interval (0 to 24 h post-dose).
- o CLR: Renal clearance
- Day 4 (Part A and Part B) and Day 7 (Part A)

DNDi RD 777/34920 DNDi- 0690- 02

Final V3.0/ Date 07 December 2020

Confidential

Page 102 of 109

- Ae0-24: Amount excreted in urine over each collection interval (0 to 24 hours post-dose on Day 4 and Day 7).
- Ae%: % of dose excreted in urine over each collection interval (0 to 24 h post-dose on Day 4 and Day 7).

# • Day 10 (Part A and Part C) and Day 5 (Part B):

- o AUC0-inf: AUC extrapolated to infinity
- AUC0-inf/D: AUC extrapolated to infinity/Dose
- o AUC0-24: Area under the concentration-time curve (AUC) from the time of dosing to 24 hours pose
- o AUC0-24/D: AUC0-24/Dose
- o Cmax,ss: Maximum concentration at steady state
- o Cmax,ss/D: Maximum concentration at steady state/Dose
- o Cmin,SS: Minimum concentration at steady state
- o Cav,ss: Average concentration at steady state
- O Degree of fluctuation: (Cmax-Cmin)/Cav.SS
- o Swing: (Cmax,SS-Cmin,SS)/Cmin,SS
- AUC0-inf,norm: AUC extrapolated to infinity divided by dose per kilogram body weight
- o AUC0-24, norm: Area under the concentration versus time curve from zero to 24 hours divided by dose per kilogram body weight
- o AUClast: Area under the concentration-time curve (AUC) from the time of dosing to the time of the last measurable concentration
- o AUClast/D: AUClast/Dose
- o AUClast,norm: AUClast divided by dose per kilogram body weight
- Cmax,ss,norm: Maximum concentration at steady state divided by dose per kilogram body weight
- $\circ$  Tmax: The time to maximum observed concentration
- o  $t_{1/2}$ : Terminal elimination half-life
- Cl/F: Clearance
- o lambda-z (kel): Elimination rate constant
- o MRTlast: Mean Residence Time from the time of dosing to the time of the last measurable concentration
- o Vz/F: Volume of distribution
- o CLss/F: Clearance at steady state
- o AUCt-inf: AUC extrapolated from t to infinity

DNDi RD 777/34920 DNDi- 0690- 02

Final V3.0/ Date 07 December 2020

Confidential

Page 103 of 109

- o %AUCextra: % AUC extrapolated from the last plasma concentration to infinity
- o Points terminal for DNDI-0690: points selected to calculate terminal elimination half-life
- Ctrough will be derived from the concentration data (Days 2-10 for Part A, days 2-/5 for Part B and days 2/4/7/10 for Part C)
- O Accumulation ratios RA (Cmax) and RA (AUC0-τ)
- O Day 10 (Part A) and Day 5 (Part B):
  - Ae0-24: Amount excreted in urine over each collection interval (0 to 24 hours post-dose).
  - Ae%: % of dose excreted in urine over each collection interval (0 to 24 h post-dose).
  - CLR: Renal clearance

If BID dosing, AUC0-10, AUC0-10/D, AUC0-10h,norm will be added on Day 1 and Day10.

Derived PK parameters will be listed along with the points used to calculate  $k_{el}$  (lower, upper and number used) and  $R^2$  adjusted. The derived PK parameters will also be summarised. The descriptive statistics presented will be N, n, arithmetic mean, geometric mean (with the exception of  $T_{max}$ ), SD, coefficient of variation (CV%), minimum, median and maximum.

**Dose Proportionality/Independence (Part A and Part B):** For Day 1 and Day 10 (Part A) OR Day 1 and Day 5 (Part B), dose proportionality will be assessed by performing a regression analysis of the log-transformed  $C_{max}$ ,  $AUC_{0-\tau}$  and  $AUC_{0-inf}$  (Day 10 for Part A and Day 5 for Part B only) values versus the log-transformed dose using the power model with a fixed effect for log(dose). For each parameter a point estimate and 95 % confidence interval (CI) will be calculated for the slope of the regression line.

For Day 10 for Part A and Day 5 for Part B, dose independence will be assessed for t½ and CL/F by performing a regression analysis of the untransformed parameters versus dose with a fixed effect for dose. For each parameter a point estimate and corresponding 95 % CI will be calculated for the slope of the regression line.

**Steady-State** (**Part A and Part B**): For each dose level, log-transformed trough concentration levels at pre-dose each day (Day 2 to Day 10 for Part A and Day 2 to Day 5 for Part B) will be subjected to a mixed effects analysis of variance (ANOVA) with study day as a fixed effect and subject as a random effect in order to establish whether and when steady-state has been attained for each dose level. Back-transformed ratios for the comparisons of each consecutive day (*i.e.* Day 3/Day 2) will be presented along with corresponding 90 % CI.

Accumulation (Part A and Part B): For each dose level, log-transformed  $C_{max}$  and  $AUC_{0-\tau}$  values on Day 1 and day 10 for Part A or Day 1 to Day 5 for Part B will be subjected to an ANOVA with study day as a fixed effect and subject as a random effect. For comparison point estimates and 90 % CI for the difference between Day 10 (Part A) or Day 5 (Part B) and Day 1 will be constructed using the residual mean square error obtained from the ANOVA for each dose level. The point and interval estimates will then be back transformed to give estimates of the ratios of the geometric least squares means and corresponding 90 % CI.

DNDi RD 777/34920 DNDi- 0690- 02

Final V3.0/ Date 07 December 2020

Confidential

Page 104 of 109

Derived relative PK Data for metabolite M5: The peak areas of M5 will be recorded and a relative comparison of the peak areas of M5 versus DNDI-0960 will be performed for each subject at each time point. The relative abundance of M5 will be expressed as percentage of DNDI-0960 (depending on the data obtained, this may be a relative abundance per time point or via relative AUC comparison via peak area integration over time). Although this is a qualitative analysis of M5, an attempt will be made on a non-quantitative level to classify the abundance of M5 in plasma of subjects compared to DNDI-0960 as major (>10%), minor (2-10%) or negligible (<2%).

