## 10.3 Discussion of Study Design, including the Choice of Control Groups

#### 10.3.1 Part A

The starting dose for this multiple dose-escalation study was selected on the basis of the results of the SAD study in human healthy volunteers: at the highest administered dose (3600 mg), the AUC $_{0-inf}$  geometric mean was 47,800 (Geometric CV%: 26.7) ng.h/mL and the  $C_{max}$  geometric mean was 2560 (Geometric CV%: 20.7) ng/mL.

Final V3.0/ Date 07 December 2020

Confidential

Page 51 of 109

DNDi RD 777/34920 DNDi- 0690- 02

Predictions of steady state exposures have been performed simulating repeated doses at the actual dose levels administered in the SAD study in healthy male subjects in fasted condition. Actual single dose data at each dose level were used to predict its own steady state levels.

The performed non-parametric super positioning assumed linearity over time following repeated dosing. The following exposures were predicted for once a day dosing at steady state:

Table 4 Geometric Mean (CV%) Key Observed in the Single Ascending Dose Study and Predicted Pharmacokinetic Parameters of DNDI-0690 in Male Healthy Volunteers

DNDI- 0690			ed Parameters (CV%)		Predicted Parameters at Steady State after Once Daily Dosing (CV%)						
	Cmax (ng/mL)	AUC(0-12) (ng.h/mL)	AUC(0-24) (ng.h/mL)	AUC(0-inf) (ng.h/mL)	Cmax (ng/mL)	AUC(0-tau) (ng.h/mL)	Accumulation Ratio				
10 mg	172 (26.9%)	1140 (46.3%)	1470 (61.4%)	1640 (77.9%)	182 (39.4%)	1570 (77.7%)	1.07 (13.9%)				
30 mg	496 (29.1%)	3530 (40.1%)	4650 (50.1%)	5270 (62.0%)	534 (35.0%)	4980 (62.8%)	1.07 (11.5%)				
150 mg	775 (25.6%)	5380 (49.4%)	7060 (66.8%)	7720 (78.4%)	827 (31.6%)	7240 (76.8%)	1.03 (8.09%)				
400 mg	1120 (24.1%)	8500 (39.4%)	11800 (53.6%)	13900 (67.5%)	1240 (32.5%)	13100 (65.8%)	1.11 (10.6%)				
1200 mg	1670 (25.2%)	13400 (35.2%)	19700 (48.9%)	25100 (63.9%)	1990 (37.2%)	23600 (64.2%)	1.20 (14.3%)				
3600 mg	2600 (18.8%)	21200 (21.6%)	32800 (24.5%)	47100 (24.2%)	3380 (18.5%)	44900 (23.5%)	1.37 (6.63%)				

Exposure after multiple dose of 400 mg OD are predicted to reach a mean (CV%) exposure of  $C_{max}$  1240 (32.5%) ng/mL and an  $AUC_{0-\tau}$  13,100 (65.8%) ng.h/mL, which remains below the maximum exposure measured after single dose without safety concerns (see Table 4). The dose of 400 mg OD is thus considered a safe starting dose for multiple dosing.

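### On Day 10/Day 5 the AUC0-inf dose-proportionality slope, and apparently the Cl/F dose-independence slope, carry residual drug from earlier doses by a factor that rises with dose

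*Protocol*

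**What the plan says.** Section 10.9.2.5.4 (PK Data), repeated in the synopsis under Dose Proportionality/Independence, sets out two regressions.

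- **Proportionality.** Log Cmax, AUC0-tau and AUC0-inf are regressed on log dose: "values versus the log-transformed dose using the power model with a fixed effect for log(dose"). AUC0-inf enters with the restriction "Day 10 for Part A and Day 5 for Part B only".
- **Independence.** On the same days, "dose independence will be assessed for t½ and CL/F by performing a regression analysis of the untransformed parameters versus dose".

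The list of last-day parameters in the same section contains both "Cl/F: Clearance" and, as a separate item, CLss/F, described as "Clearance at steady state". Neither has a formula. The test names CL/F. AUC0-inf is not among the Day 1 parameters, so the only AUC0-inf available follows repeated dosing. The abbreviations list starts AUC0-inf at the dosing time and mentions no correction for drug already present. Section 10.9.2.2 classes Day 10 AUC0-inf as a main parameter and Cl/F as exploratory. Section 10.3.1 anticipates steady state by about the third day of dosing.

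**The concern.** At steady state the AUC that reflects one dose is AUC0-tau, and clearance is Dose/AUC0-tau. Integrating from the last dose to infinity adds the tails of all earlier doses. Dose divided by that larger area is too small a clearance.

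A constant excess would leave a log-log slope unchanged. Here it is not constant: the protocol expects more accumulation at higher doses. AUC0-inf would therefore look closer to dose-proportional than it is, and Dose/AUC0-inf closer to dose-independent. Section 8.6.1 reports sub-proportional exposure after single doses, and this is the feature that the two regressions are meant to describe. The report would also hold two conflicting AUC slopes from the same profiles, with nothing to say which one is distorted.

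**Working it through.** **Inputs.** Section 10.3.1, Table 4, geometric means in ng·h/mL:

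| Dose (mg) | Single-dose AUC0-24 | Single-dose AUC0-inf | Predicted steady-state AUC0-tau | Stated accumulation ratio |
|---|---|---|---|---|
| 400 | 11800 | 13900 | 13100 | 1.11 |
| 1200 | 19700 | 25100 | 23600 | 1.20 |
| 3600 | 32800 | 47100 | 44900 | 1.37 |

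The half-life range is 4.547 to 12.144 h (section 8.6.1). It is not given by dose.

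**Step 1: reproduce the plan's figure.** Accumulation ratio = AUC0-tau / AUC0-24: 13100/11800 = 1.110, 23600/19700 = 1.198, 44900/32800 = 1.369. These match Table 4. The 10, 30 and 150 mg rows also agree (1.068, 1.071, 1.025 against 1.07, 1.07, 1.03).

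**Step 2: carry-over in last-day AUC0-inf.** Assume superposition, as the protocol does for Table 4, and a log-linear decline after 24 h. Then

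last-day AUC0-inf = single-dose AUC0-inf × [1 + f/(1 − q)],

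where f = 1 − AUC0-24/AUC0-inf and q = exp(−24·ln 2/t½). From Table 4, f = 0.151, 0.215 and 0.304. Because half-life by dose is not given, q is varied; the one-compartment case sets q = f.

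| Assumption | Factor at 400 / 1200 / 3600 mg | Last-day AUC0-inf |
|---|---|---|
| t½ 4.547 h | 1.155 / 1.221 / 1.312 | 16056 / 30643 / 61778 |
| t½ 8 h | 1.173 / 1.246 / 1.347 | 16300 / 31271 / 63443 |
| t½ 12.144 h | 1.203 / 1.288 / 1.407 | 16716 / 32340 / 66273 |
| One compartment | 1.178 / 1.274 / 1.436 | 16374 / 31980 / 67634 |

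**Step 3: power slope, 400-3600 mg.** The three doses are equally spaced on the log scale, so the least-squares slope is ln(AUC at 3600/AUC at 400)/ln 9.

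- AUC0-tau: ln(44900/13100)/ln 9 = 0.561.
- Single-dose AUC0-inf: ln(47100/13900)/ln 9 = 0.555.
- Last-day AUC0-inf: 0.613, 0.618 and 0.627 for the three half-lives, and 0.646 for one compartment.

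The shift from 0.555 is 0.06 to 0.09. Over 400-1200 mg alone, the slope moves from 0.538 to 0.59-0.61. As a cruder cross-check, multiplying Table 4 AUC0-tau by its accumulation ratio gives 0.656.

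**Step 4: clearance on dose, if Cl/F = Dose/AUC0-inf.**

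| Clearance (L/h) | 400 mg | 1200 mg | 3600 mg | Slope per 1000 mg |
|---|---|---|---|---|
| Dose / single-dose AUC0-inf | 28.8 | 47.8 | 76.4 | 14.2 |
| CLss/F = Dose / AUC0-tau | 30.5 | 50.8 | 80.2 | 14.8 |
| Dose / last-day AUC0-inf, t½ 4.547 h | 24.9 | 39.2 | 58.3 | 9.86 |
| Dose / last-day AUC0-inf, one compartment | 24.4 | 37.5 | 53.2 | 8.43 |

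Against the single-dose slope (14.21 before rounding), the loss is 1 − 9.86/14.21 = 31% to 1 − 8.43/14.21 = 41%. Over 400-1200 mg the slope falls from 23.79 to between 17.81 and 16.37, a loss of 25% to 31%. The point therefore does not depend on the optional 3600 mg dose.

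**The case against.** **The valid analysis is already there.** The same sentence fits the power model to Cmax and AUC0-tau, and CLss/F is derived. This stands: it confines the defect to AUC0-inf and, apparently, Cl/F. It does not make the AUC0-inf slope right.

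**Cl/F is undefined.** A reader might infer that the clearance test is certainly wrong. The protocol does not go that far. If Cl/F is to be Dose/AUC0-tau, it duplicates CLss/F and this half falls away. Listing the two separately suggests otherwise, but that is inference. The AUC0-inf half does not depend on it.

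**Dose choice.** A reader might infer that the bias would mislead escalation. Section 10.2.1 bases escalation on safety data with Cmax and AUC0-24, and section 10.2.2.3 sets its exposure limits on AUC0-tau and Cmax. No rule uses these slopes.

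**Size against noise.** Assuming six active subjects at each of 400, 1200 and 3600 mg and the Table 4 CVs for AUC0-tau, the slope's 95% CI half-width is about ±0.28. The shift lies well inside it, and 0.56 and 0.65 both indicate sub-proportionality. This limits the practical weight. But the shift is systematic, and both slopes come from the same subjects, so sampling error does not excuse it.

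**Point values.** It is tempting to quote the one-compartment factors (1.18, 1.27, 1.44) as exact and as the ratio of AUC0-inf to AUC0-tau. They are relative to single-dose AUC0-inf. Against Table 4 AUC0-tau the same areas give 16.4/13.1 = 1.25, 32.0/23.6 = 1.36 and 67.6/44.9 = 1.51. At 3600 mg the one-compartment case is the upper end of the range.

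**Part B.** A reader might infer that an impossible single-dose regression is planned. The heading covers Parts A and B together, so pooling is the natural reading; it only needs stating.

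**Conclusion.** The concern holds for AUC0-inf, and conditionally for Cl/F. The protocol fixes a dose-proportionality test on an AUC that includes carry-over, and its own Table 4 implies that the carry-over rises with dose. The AUC0-inf power slope over 400-3600 mg would read about 0.61-0.65 instead of about 0.56. If Cl/F is Dose/AUC0-inf, the clearance slope on dose would be understated by about 31-41% (25-31% over 400-1200 mg).

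These figures rest on Table 4 geometric means, superposition, once daily dosing at steady state, and a half-life within the stated range or one-compartment kinetics. The consequence is limited to secondary and exploratory PK conclusions. The Cmax, AUC0-tau and t½ analyses, escalation within the trial and the primary safety endpoints are untouched.

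**What to change.** In section 10.9.2.5.4 and the synopsis, for Day 10 (Part A) and Day 5 (Part B):

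1. Remove AUC0-inf from the power model and rely on AUC0-tau and Cmax,ss.
2. Name CLss/F, defined as Dose/AUC0-tau, instead of CL/F in the dose-independence test. Keep t½.
3. Keep last-day AUC0-inf and Cl/F as descriptive only, labelled as including carry-over, and give the Cl/F formula.
4. Apply items 1 and 2 directly to once daily cohorts. Under the optional BID regimen the intervals are 10 h and then 14 h, and Day 10 has only a morning dose (section 10.5.3.1), so Dose/AUC0-10 is not steady-state clearance. Analyse a BID cohort separately or leave it out of the clearance regression.
5. State that Part B's single dose level is pooled with Part A in one model.

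The cost is a wording change in the protocol and SAP. For once daily cohorts every quantity needed is already derived; no sample, visit or subject is added.
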